## 7.2.2 Assessments and Treatment

## Day 7 ± 3 Days (day of infusion)

#### Pre-infusion:

- Inclusion/exclusion criteria review.
- Review and record any changes in medical history, including concomitant medications from screening.
- Confirm Informed Consent Form (ICF) is complete with signature of subject, or legal guardian & witness.
- Measure and record weight and vital signs (oral temperature, blood pressure, pulse rate) after subjects rest quietly in a supine or semi-recumbent position.
- Final Formulation Skin Test. Performed prior to infusion (Appendix C)
- Physical and Cardiac Examination
- Draw and store blood samples for IgA, IgE, IgG, IgM and for Lymphocyte Proliferation Panel
- Place an IV line in the upper extremity or hand with 0.9% sodium chloride running to keep the vein open

## During infusion:

- IV infusion of the study product or placebo
- Monitoring for any signs of adverse reaction, record adverse event/s and concomitant medications
- Record vital signs every 2 hours, and as clinically indicated
- Continuous ECG monitoring during infusion of study product
- Pulse oximetry continuously during and for 2 hours post infusion

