## **6** INVESTIGATIONAL PRODUCT

## 6.1 Formulation, Packaging, Preparation, Randomization of aMBMC or Placebo

The study will enroll a minimum of 20 subjects and will consist of 2 cohorts. Enrolled subjects will be randomized at 1:1 into an experimental group (n=15) or a placebo group (n=15). Subjects in the experimental group will receive 1.5 million cells per kg and subjects in the placebo group will receive 1 mL/kg Lactated Ringer's Solution.

Once the subject is randomized into one of the two cohorts, the cells or placebo will be prepared. Within 8 hours of infusion, the appropriate number of cells will be thawed at the study site pharmacy and re-suspended in Lactated Ringer's Solution (LRS) at a concentration of 1x10^6 cells/mL Subjects in placebo group will receive LRS at a volume of 1 mL/kg. The study solution (cells or placebo) will be labeled to indicate that it is an investigational agent and will contain a subject's information, date, and time of formulation.

After discharge, subjects will have safety and efficacy evaluations as per Appendix A.

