#### 6.2 IV Administration of aMBMC or Placebo

On the day of infusion, prior to study product administration, a skin test will be administered using 0.1 mL aliquot of the Final Formulation (Appendix C).

An intravenous line will be placed into an appropriate vein on the upper extremity or hand with 0.9% sodium chloride solution running to keep the vein open. The study solution described above will be taken up in an 18-gauge needle into a 60 mL syringe with an eccentric (offset) tip. The needle will be removed and infusion tubing will be attached to the syringe. The syringe with infusion tubing will be placed in a metered dose syringe pump positioned horizontally with the syringe rotated such that the syringe tip is at the lowest position. The product will be infused intravenously into the subject's arm at a constant rate of approximately 2 mL/min. The applicable volume for the target dose will be delivered within  $\pm$  2 mL. Depending on subject's weight, up to three 60 mL syringes of product may be infused. After the entire product volume is delivered, 25 mL of LRS (without cells) will be infused at 2 mL/min to deliver cells from the infusion line for more accurate dosing. Subjects in the placebo group will receive intravenous LRS. Their syringes will be labeled as above to preserve blinding and followed by 25 mL of LRS infusion as above.

If the subject has an adverse reaction during the infusion, the infusion may be interrupted or slowed according to the severity of the reaction. All appropriate treatment will be given to reduce any discomfort and ensure the subject's safety. The infusion may be restarted, if interrupted, if the subject is not considered to be at risk by the Investigator and the subject consents.

All subjects will receive the follow-up tests and evaluations as per Appendix A.

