#### 7 STUDY ASSESSMENTS AND SCHEDULE

#### 7.1 **General Assessments**

## **Clinical Assessments**

- Complete medical history, including medication use and lifestyle history •
- Physical and cardiac examination, including vital signs (temperature, systolic blood pressure/diastolic • blood pressure, weight, heart rate, respiratory rate)
- Cardiac Examination •
- Composite of all-cause mortality, admission for worsening HF and all-cause admissions. •
- Exercise capacity: 6 minute walk distance •
- Kansas City Cardiomyopathy Questionnaire (KCCQ)(Appendix B)
- New York Heart Association (NYHA) Classification (Appendix B)

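### The 2-hourly vital-sign interval set for the infusion is longer than most planned infusions, so it does not assure a scheduled blood pressure, temperature or respiratory-rate reading before the infusion ends

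*Combined protocol and SAP*

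**What the plan says.** Section 7.2.2 divides the infusion day into pre-infusion, during-infusion and post-infusion lists.

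- **Before:** one set of vital signs, at no stated time before the start.
- **During:** "Record vital signs every 2 hours, and as clinically indicated". The same list requires continuous ECG, watching for adverse reactions, and "Pulse oximetry continuously during and for 2 hours post infusion".
- **After:** vital signs every 2 hours until discharge, with at least 6 hours of observation (± 30 minutes) or until stable.

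Section 6.2 sets the pace. Product runs "at a constant rate of approximately 2 mL/min"; depending on weight, "up to three 60 mL syringes of product may be infused"; then "25 mL of LRS (without cells) will be infused at 2 mL/min". If there is a reaction, "the infusion may be interrupted or slowed according to the severity of the reaction". The cell dose is 1.5 million cells/kg at 1 million cells/mL, and section 6.1 gives the comparator volume: "Subjects in placebo group will receive LRS at a volume of 1 mL/kg".

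Section 7.1 includes "blood pressure, weight, heart rate, respiratory rate" with temperature among the vital signs, and the Appendix A footnote gives the same components. That footnote places the 2-hourly readings after the infusion. The Day 90 list in section 7.3, which covers the crossover infusion, names vital signs once and has no during-infusion list.

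**The concern.** Vital signs have their own line in the during-infusion list, so readings were evidently wanted in that period. An interval longer than the infusion need not produce one. A site could follow the schedule exactly and have no routine blood pressure, temperature or respiratory rate after exposure begins and before it ends.

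Safety is the primary objective, and section 4.2 lists both procedural complications and vital signs under the primary endpoint. The subjects have reduced ejection fraction and NYHA class II-III symptoms, and may be taking drugs that lower blood pressure. The practical loss concerns a subject without symptoms whose pressure or temperature changes while product is running. Staff may slow or stop the infusion for a reaction, but that choice is open only until the infusion ends.

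**Working it through.** The plan states no infusion duration, so there is no figure of its own to reproduce. Duration follows from sections 6.1 and 6.2.

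**Formulas** (w = weight in kg, rate 2 mL/min throughout)

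- Flush: 25 / 2 = 12.5 min.
- Cells: 1.5 million cells/kg at 1 million cells/mL = 1.5 mL/kg, so minutes = 1.5w / 2 + 12.5 = 0.75w + 12.5.
- LRS: 1 mL/kg, so minutes = 0.5w + 12.5.

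**Planned duration including flush**

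| Weight | Cells | LRS |
|---|---|---|
| 60 kg | 57.5 min | 42.5 min |
| 80 kg | 72.5 min | 52.5 min |
| 100 kg | 87.5 min | 62.5 min |
| 120 kg | 102.5 min | 72.5 min |

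Three full syringes are 180 mL, which is the cell volume at 120 kg: 180 / 2 + 12.5 = 102.5 min. With the +2 mL delivery tolerance it is 182 / 2 + 12.5 = 103.5 min.

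**When would the infusion reach 120 minutes?**

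- *Weight:* if more than three syringes were allowed, cells reach 120 min at (120 − 12.5) / 0.75 = 143.3 kg (215 mL), and LRS at (120 − 12.5) / 0.5 = 215 kg.
- *Rate:* at 180 mL, with product and flush slowed together, 205 / 120 = 1.71 mL/min. With only the product slowed, 180 / 107.5 = 1.67 mL/min. For an 80 kg cell recipient with only the product slowed, 120 / 107.5 = 1.12 mL/min.
- *Pauses:* the room for syringe changes or interruptions is 120 − 102.5 = 17.5 min at 180 mL, and 120 − 72.5 = 47.5 min for an 80 kg cell recipient.

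**Where could a 2-hourly reading fall?** The start of the clock is not stated.

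- *From infusion start:* a reading at time zero precedes exposure. The next is at 120 min, after the flush.
- *From the pre-infusion set, taken g minutes before the start:* the next reading is 120 − g minutes into the infusion. It falls inside only if g exceeds 17.5 min (180 mL) or 47.5 min (80 kg, cells). No section fixes g. The only timed preparatory step is the skin-test reading in Appendix C, at 10-15 minutes.
- *Appendix A footnote:* 2-hourly readings are placed after the infusion.

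None of these readings of the text assures a scheduled value during the infusion.

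**Would 15- and 30-minute readings fit?** A 30-minute reading precedes the end of the flush if w exceeds (30 − 12.5) / 0.5 = 35 kg on LRS, or (30 − 12.5) / 0.75 = 23.3 kg on cells. That should cover essentially any adult.

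**The case against.** The strongest reply is that the plan already calls for vital signs in this period and monitors subjects closely. The instruction sits under a during-infusion heading, so a sensible site would take a set. If the pre-infusion list is worked in order, the skin test, examinations, blood draws and line placement follow the vital signs. A gap of more than 17.5 minutes is then likely, which would put a reading inside a 180 mL infusion. Rhythm, heart rate and oxygen saturation are watched continuously, and oximetry bears on the early lung entrapment described in sections 2.2 and 2.6. A positive skin test excludes the subject. Sections 2.7 and 2.8.1 report reassuring intravenous experience: 19 STEMI patients treated with the sponsor's cell type without SAEs, and another product given safely at up to 5 million cells/kg.

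Much of this stands, and it limits the size of the point. It does not supply the missing reading. The order of the pre-infusion steps is not mandated, and the 47.5-minute gap needed for an 80 kg cell recipient is much less certain. Earlier experience bears on how often a reaction may occur, not on whether the schedule would record one.

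A second reply is that 102.5 minutes is not a firm maximum. That is right: the rate is approximate, the three-syringe figure may describe expected use and not a cap, and eligibility sets no upper weight.

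A reader might infer that subjects go unmonitored, or that no vital signs will be taken during infusion. The documents do not support either, given the continuous monitoring and the provision for readings when clinically indicated. Nor do they support calling this a numerical error, since no figure in the plan is wrong.

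**Conclusion.** The point holds as a modest safety gap that should be closed. At the planned rate, an infusion with flush takes about 102.5 minutes at 180 mL and 72.5 minutes for an 80 kg cell recipient. The 2-hour rule therefore does not assure a scheduled blood pressure, temperature or respiratory rate before the infusion ends. A reading may still occur, depending on site practice.

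This rests on three assumptions: a rate near 2 mL/min, no slowing or interruption, and either a three-syringe cap or a cell recipient below about 143 kg. The pre-infusion list in section 7.2.2 leaves out respiratory rate, but nothing here depends on that, because section 7.1 and Appendix A both count it as a vital sign.

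**What to change.** In the during-infusion list of section 7.2.2, replace the 2-hour interval with blood pressure, heart rate, temperature and respiratory rate at fixed times from infusion start: at minimum 15 minutes, 30 minutes and end of infusion. The sponsor can set any further interval for longer infusions. Name the four measures, because section 7.1 and Appendix A also count weight as a vital sign and re-weighing a subject on a pump makes no sense. Keep the provision for readings when clinically indicated, and keep the 2-hourly readings for the post-infusion period.

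Use the same timetable for cells and LRS, at both the Day 7 and Day 90 infusions, with a cross-reference in the Day 90 list of section 7.3 and in the Appendix A footnote. If a further interval makes the number of readings differ by arm, list the in-infusion values separately from the section 9.2 summary of change to the maximum post-administration value. More readings give more chances of a high maximum, and cells run longer than LRS at the same weight.

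Cost: a short text change, a CRF row and a few minutes of nursing time. The minimum schedule is 3 readings × 2 infusions = 6 per subject, or 6 × 20 = 120 across 20 subjects, taken by staff already monitoring ECG and oximetry.

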#### Post- infusion:

- 12-lead ECG
- Monitoring for any signs of adverse reaction, record adverse event/s and concomitant medications
- Record vital signs every 2 hours till discharge
- Continuous ECG monitoring for 2 hours
- Pulse oximetry continuously for 2 hours
- Cardiac biomarkers (CK and CK-MB fraction, troponin I).
- Serum/plasma stored for VEGF, FGF, NT-proBNP, troponin
- Subjects will be observed for a minimum of 6 hours ± 30 minutes post infusion or until deemed stable in the opinion of the investigator
- Subject is free to ambulate according to investigators discretion
- Physical exam, prior to discharge if clinically stable
- Provide subject or responsible individual accompanying the subject with the phone number for contacting the study nurse and/or investigator for any questions, concerns or changes in health status.

## 7.3 Follow-up Assessments

## Day 30 (±7) days post-infusion

- Measure and record vital signs
- 12-lead ECG
- Pulse Oximetry
- 24 hour Holter ECG recording or ICD assessment
- Record the composite of all-cause mortality, admission for worsening HF and all-cause admissions, and concomitant medication use
- Physical and cardiac examination
- Clinical labs: serum chemistry including BUN & creatinine, CBC with diff, LFT's, total protein and albumin
- Cardiac biomarkers (CK and CK-MB fraction, troponin I)
- Serum/plasma stored for VEGF, FGF, NT-proBNP, troponin
- Kansas City Cardiomyopathy Questionnaire (KCCQ)
- New York Heart Association (NYHA) Classification
- 6 minute walk test

## Day 60 (±7) days post infusion)

- Measure and record vital signs
- 12-lead ECG
- Pulse Oximetry
- 24 hour Holter ECG monitoring or ACD assessment
- Record the composite of all-cause mortality, admission for worsening HF and all-cause admissions, and concomitant medication use
- Physical and cardiac examination
- Clinical labs: serum chemistry including BUN & creatinine, CBC with diff, LFT's, total protein and albumin
- Cardiac biomarkers (CK and CK-MB fraction, troponin I)
- Serum/plasma stored for VEGF, FGF, NT-proBNP, troponin
- Draw and store blood samples for IgA, IgE, IgG, IgM and for Lymphocyte Proliferation Panel
- Kansas City Cardiomyopathy Questionnaire (KCCQ)
- New York Heart Association (NYHA) Classification
- Spirometry/DLCO
- 6 minute walk test

## Day 90 (±7) days post initial infusion, day of crossover infusion)

- Measure and record vital signs
- Final Formulation Skin Test. Performed prior to infusion (Appendix C)
- 12-lead ECG
- Pulse Oximetry
- 24 hour Holter ECG monitoring or ACD assessment
- Record the composite of all-cause mortality, admission for worsening HF and all-cause admissions, and concomitant medication use
- Physical and cardiac examination
- Clinical labs: serum chemistry including BUN & creatinine, CBC with diff, LFT's, total protein and albumin,
- Cardiac biomarkers (CK and CK-MB fraction, troponin I)
- Serum/plasma stored for VEGF, FGF, NT-proBNP, troponin
- Draw and store blood samples for IgA, IgE, IgG, IgM and for Lymphocyte Proliferation Panel

- Kansas City Cardiomyopathy Questionnaire (KCCQ)
- New York Heart Association (NYHA) Classification
- Spirometry/DLCO
- 6 minute walk test
- Cardiac MRI, with delayed contrast enhancement
- Full 2D and Doppler transthoracic echocardiography with speckle-tracking
- Pregnancy test for women of childbearing potential

#### 7.4 Early Termination Visit

- Measure and record weight and vital signs
- 12-lead ECG
- Pulse Oximetry
- 24 hour Holter ECG monitoring or ACD assessment
- Record the composite of all-cause mortality admission for worsening HF and all-cause admissions, and concomitant medication use
- Physical and cardiac examination
- Clinical labs: serum chemistry including BUN & creatinine, CBC with diff, LFT's, total protein and albumin
- Serum/plasma stored for VEGF, FGF, NT-proBNP, troponin
- Blood sample for IgA, IgE, IgG, IgM and for Lymphocyte Proliferation Panel
- 6 minute walk test
- Kansas City Cardiomyopathy Questionnaire (KCCQ)
- New York Heart Association (NYHA) Classification
- Cardiac MRI, with delayed contrast enhancement
- Full 2D and Doppler transthoracic echocardiography with speckle-tracking

The same follow-up visits will be performed after the crossover phase.

#### 8 ASSESSMENT OF SAFETY

#### 8.1 Safety Parameters

Safety assessments will consist of monitoring and recording adverse treatment events. Changes in clinical laboratory, clinical status and physical examination values will be used for evaluation.

#### 8.1.1 Adverse Event (AE)

ICH E6 defines an AE as any untoward medical occurrence in a subject or clinical investigation subject administered a pharmaceutical product regardless of its causal relationship to the study stem cell administration. An AE can therefore be any unfavorable and unintended sign (including an abnormal laboratory finding), symptom, or disease temporally associated with the use of medicinal (investigational) product. The occurrence of an AE may come to the attention of study personnel during study visits and interviews of a study recipient presenting for medical care, or upon review by a study monitor.

All AEs including local and systemic reactions not meeting the criteria for "serious adverse events" will be captured on the appropriate CRF. Information to be collected includes event description, time of onset, clinician's assessment of severity, relationship to study product (assessed only by those with the training and authority to make a diagnosis) which would include MD, DO, PA or NP and time of resolution/stabilization of the event. All AEs occurring while on study must be documented appropriately regardless of relationship. All AEs will be followed to adequate resolution.

Any medical condition that is present at the time that the subject is screened will be considered as baseline and not reported as an AE. However, if it deteriorates at any time during the study, it should be recorded as an AE.

All AEs must be graded for severity and relationship to study product.

**Severity of Event:** All AEs will be assessed by the clinician using the following grading system of AE intensity.

- Mild: events require minimal or no treatment and do not interfere with the subject's daily activities.
- Moderate: events result in a low level of inconvenience or concern with the therapeutic measures. Moderate events may cause some interference with functioning.
- Severe: events interrupt a subject's usual daily activity and may require systemic drug therapy or other treatment. Severe events are usually incapacitating.
- Life threatening: any adverse drug experience that places the subject, in the view of the investigator, at immediate risk of death from the reaction as it occurred, i.e., it does not include a reaction that had it occurred in a more severe form, might have caused death.

Changes in the severity of an AE will be documented to allow an assessment of the duration of the event at each level of intensity to be performed. Adverse events characterized as intermittent require documentation of onset and duration of each episode.

**Relationship to Study Products:** The clinician's assessment of an AE's relationship to investigational product is part of the documentation process, but it is not a factor in determining what is or is not reported in the study. If there is any doubt as to whether a clinical observation is an AE, the event will be reported. All AEs must have their relationship to investigational product assessed. In a clinical trial, the investigational product must always be suspect. To help assess, the following guidelines are used.

- Related There is a plausible temporal relationship between the onset of the AE and administration of the investigational product, and the AE cannot be readily explained by the subject's pre-existing clinical state, intercurrent illness, or concomitant therapies; and/or the AE follows a known pattern of response to the investigational product; and/or the AE abates or resolves upon discontinuation of the investigational product and, if applicable, reappears upon re-challenge.
- Not Related There is good evidence that the AE has an etiology other than the investigational product (e.g., pre-existing medical condition, underlying disease, intercurrent illness, or concomitant medication); and/or the AE has no plausible temporal relationship to administration of the investigational product (e.g., cancer diagnosed 2 days after treatment).

## 8.1.2 Serious Adverse Event (SAE)

An SAE is an AE that results in any of the following outcomes:

- Death (i.e., the AE actually causes or leads to death)
- Life threatening event (i.e., the AE, in the view of the Investigator, places the subject at immediate risk of death)
- Requires or prolongs inpatient hospitalization
- Results in persistent or significant disability/incapacity (i.e., the AE results in substantial disruption of the subject's ability to conduct normal life functions)
- A congenital anomaly/birth defect in a neonate/infant born to a mother exposed to the investigational product(s)

Any other important medical event that may not result in death, be life threatening, or require hospitalization, may be considered a serious adverse experience when, based upon appropriate medical judgment, the event may jeopardize the subject and may require medical or surgical intervention to prevent one of the outcomes listed above. Examples of such medical events include allergic bronchospasm requiring intensive treatment in an emergency room or at home, blood dyscrasias or convulsions that do not result in inpatient hospitalization.

The terms "severe" and "serious" are not synonymous. Severity refers to the intensity of an AE (as in mild, moderate, or severe pain); the event itself may be of relatively minor medical significance (such as severe headache). "Serious" is a regulatory definition and is based on subject or event outcome or action criteria

usually associated with events that pose a threat to a subject's life or vital functions. Seriousness (not severity) serves as the guide for defining regulatory reporting obligations.

Severity and seriousness will be independently assessed when recording AEs and SAEs on the CRF.

## 8.2 Methods and Timing for Assessing, Recording, and Analyzing Safety Parameters

The Investigator is responsible for ensuring that all study-emergent AEs and SAEs (as defined in Section 7.1) are recorded on the CRF and reported to the sponsor in accordance with protocol instructions. For each SAE observed, the investigator will obtain all of the information available about the event, including (but not limited to): hospital discharge diagnoses, hospital discharge note, death certificate, appropriate laboratory findings (including autopsies and biopsy results), and clinical examinations (including radiological examinations and clinical consultations).

